**Perceptual Training to Improve Listeners' Ability to Understand Speech Produced by
Individuals With Dysarthria**

NCT04897711

Protocol Summary and Statistical Analysis Plan

**This file was created on 7/11/24
IRB clearance to complete this work was granted 3/26/21**

Experimental Protocol

Participants attended a single research session, lasting about two hours, at the Motor Speech Disorders Lab (MSDLab) at Florida State University or the Human Interaction Lab at Utah State University. After providing informed consent, participants completed a brief demographic survey, followed by the perceptual training protocol. The participants then completed the Words-in-Noise (WIN) test and the cognitive assessments using the NIH Toolbox Sensation and Cognition Batteries. At the time of data collection, adherence to health and safety protocols for COVID-19 was observed, including social distancing, mask-wearing, temperature monitoring, and a health questionnaire relevant to COVID-19 exposure risks. Prior to initiating the perceptual training task, participants were fitted with headphones and presented with a short audio clip. They were asked to adjust the volume to a comfortable listening level, and this volume was maintained throughout the perceptual task.

Perceptual Training Protocol. The study utilized a lexically-guided perceptual training protocol composed of three phases: pretest, familiarization, and posttest. These phases were designed to evaluate initial intelligibility and intelligibility change post-training. Participants, equipped with headphones and seated in a listening carrel, were randomly assigned to one of the speaker-specific training conditions. Instructions for each phase of the task were displayed on the computer screen. For the pretest, participants were informed that the speech samples they would hear might be difficult to understand and were asked to transcribe each phrase ($n = 20$) after hearing it once. They were encouraged to make their best guess if uncertain. Following the pretest, the familiarization phase required participants to listen to the same speaker's audio recordings of the Grandfather Passage, segmented into 35 sentences or phrases, while following along the orthographic transcription of each segment presented on the screen. They were able to advance to subsequent segments at their own pace. The final posttest phase was identical in structure to the pretest, except participants were asked to transcribe 60 new phrases spoken by the same speaker. Each phase of the perceptual training protocol was self-paced and untimed. On average, participants took approximately 30 minutes to complete the perceptual training protocol.

Hearing and Cognitive Assessment with NIH Toolbox. The NIH Toolbox (Weintraub et al., 2013) was administered via an iPad Pro to assess hearing and cognitive abilities. The WIN test was administered from the Sensation Battery to estimate auditory signal processing under challenging listening conditions. The Cognitive Battery includes a variety of tasks that estimate specific cognitive-linguistic skills, including working memory, inhibitory control, cognitive flexibility, processing speed, and vocabulary knowledge. The specific tasks used to quantify each construct are detailed briefly in Table 3. The administration of these tasks adhered closely to the NIH Toolbox guidelines with slight modifications to maintain social distancing.

Table 1. Tasks used by the NIH Toolbox Cognition Battery to quantify the hearing and cognitive-linguistic predictors

Variable	Description of the Task
Hearing	The WIN test presents a series of monosyllabic words embedded in a background of steady-state speech babble noise. After each presentation, participants are instructed to focus on the target words and repeat them back as accurately as possible. The signal-to-noise ratio (SNR) starts at an easier level and progressively becomes more challenging, providing a gradient measure of speech recognition thresholds in noisy environments.
Working memory	To estimate working memory capacity, a list sorting memory test was used. In each trial, a series of pictures from two different categories (e.g., food and animals) is presented one at a time. At the end of the trial, participants are instructed to recall the names of the pictures from one

Inhibitory control of attention	category first, in size order (smallest to largest). Participants then complete the same task with the pictures from the other category. To obtain estimates of each participant's inhibitory control of attention, a flanker test was administered. In this task, a row of arrows is presented, and the participant is instructed to select the direction in which the middle arrow points (right or left). Distractor arrows sometimes point in the same or opposite direction.
Cognitive flexibility	A dimensional change card sort test was administered to measure cognitive flexibility. This task presents a pair of pictures that differ along two dimensions relative to a target picture. The participant is instructed to select the test picture that matches the target picture based on one dimension. After several trials, the participant sorts the images based on the other dimension.
Processing speed	A pattern comparison test yields estimates of processing speech. In this task, a pair of pictures is presented, and the participant is instructed to quickly determine whether the pictures are the same while trying not to make mistakes.
Vocabulary knowledge	A picture vocabulary test was administered to obtain estimates of vocabulary knowledge. Four pictures are presented, and the participant hears a word spoken aloud. The participant is instructed to select the picture that matches the spoken word.

Statistical Analysis Plan

Analyses for this project were stratified into two main analyses, based on the subsample: 1) younger listeners and 2) older listeners. Both plans are similar with transcript analyses with Autoscore and statistical analyses that include testing for changes from pretest ("initial intelligibility") and to posttest. In addition, we will perform predictive analyses to understand these patterns more fully.

Younger Listeners

Transcript Analysis.

Listener transcriptions from both the pretest and posttest phases will be evaluated for accuracy using Autoscore, an open-source computer-based tool for automated intelligibility scoring (<http://autoscore.usu.edu>; Borrie et al., 2019). The Autoscore settings were calibrated to score a word as accurately transcribed, not only when it matched the target word but also when variations were due to tense changes or pluralization. Additionally, homophonic errors and prevalent spelling mistakes were scored as accurate utilizing a built-in list of commonly misspelled words. Each listener's performance was quantified by calculating the percentage of words correctly transcribed (PWC) in both testing phases, yielding a pretest PWC score and a posttest PWC score for each listener. These PWC scores were used to quantify initial intelligibility (pretest PWC) and intelligibility improvement (posttest PWC after accounting for pretest PWC).

Statistical Analyses.

Initial analyses will investigate distributions of the variables, assess for baseline differences, test for changes from pretest to posttest, and calculate correlations between

variables of interest. Descriptive statistics (means and standard deviations) will be calculated for all variables of interest (e.g., cognitive measures, intelligibility), and baseline differences between conditions were tested using Kruskal-Wallis Rank Sum tests. Paired-samples t-tests will be used to test for average intelligibility improvement from pretest to posttest with effect sizes estimated with Cohen's d for each speaker condition. Lastly, Pearson correlations will highlight relationships between each cognitive measure and their relationship with intelligibility (both initial and improvement) by speaker condition.

Predictive modeling—using elastic net regression models—will assess the ability of the cognitive measures to predict both initial intelligibility and intelligibility improvement. Model-specific hyper-parameters will be selected based on 10-fold cross-validation. Predictive models will be run separately for each speaker condition. For each speaker, two model specifications will be used: 1) main effects only and 2) main effects and all two-way interactions. The model predictions and variable importance metrics, as well as post hoc assessment of predictions, will inform on the nature of the important interactions. Predictive accuracy includes the root mean squared error (RMSE) and R^2 values for the cross-validated predictions. Variable importance will be extracted from each model using a permutation method wherein each variable is randomly permuted, and the difference in predictive accuracy between the observed variable and its randomly permuted counterpart was derived.

All analyses will be completed in the R statistical environment version 4.2.0 or higher.

Older Listeners

Transcript Analysis.

Listener transcriptions from both the pretest and posttest phases will be evaluated for accuracy using Autoscore, an open-source computer-based tool for automated intelligibility scoring (<http://autoscore.usu.edu>; Borrie et al., 2019). The Autoscore settings were calibrated to score a word as accurately transcribed, not only when it matched the target word but also when variations were due to tense changes or pluralization. Additionally, homophonic errors and prevalent spelling mistakes were scored as accurate utilizing a built-in list of commonly misspelled words. Each listener's performance was quantified by calculating the percentage of words correctly transcribed (PWC) in both testing phases, yielding a pretest PWC score and a posttest PWC score for each listener. These PWC scores were used to quantify initial intelligibility (pretest PWC) and intelligibility improvement (posttest PWC after accounting for pretest PWC).

Statistical Analysis.

Initial analyses of the data will include descriptive statistics for the variables of interest, testing for differences in listener cognition between the speaker conditions, testing for average intelligibility improvement between pretest and posttest for the speakers, and calculating correlations between all variables of interest. First, descriptive statistics for listener age and cognitive scores will be calculated for the speaker conditions to ensure that the listeners assigned to each condition are equal. Differences in these variables between the speaker conditions will be tested using the Wilcoxon Rank Sum test since the data did not meet statistical assumptions for parametric testing. Descriptive statistics for pretest and posttest PWC scores for both speaker conditions will also be calculated. Intelligibility improvement between the pretest and posttest will be evaluated for each speaker condition using repeated-measures ANOVA with Cohen's d effect size estimates to test for significant and meaningful intelligibility change due to the perceptual training. Pearson correlation coefficient analyses will be conducted for each speaker condition to assess the correlation between the variables of interest (e.g., cognitive scores, intelligibility).

Elastic net regression models will be used to assess how well the cognitive measures and hearing acuity predict initial intelligibility and intelligibility improvement. Separate elastic net models will be run for each speaker condition as well as for each speaker for initial intelligibility and intelligibility improvement. Therefore, a total of four elastic net models will run during this analysis. Specification of the model includes all main effects as well as all two-way interactions between the variables. The elastic net models will be evaluated using the model accuracy and variable importance metrics. Post hoc assessments will also be conducted to evaluate the nature of the important main effects and interactions. Root mean squared error (RMSE) and R² will be used to evaluate the predictive accuracy of the cross-validated predictions to incentivize the model to find the predictive relationships that will likely generalize to untrained data. Variable importance will be extracted from each model using permutation. The main effects and interactions selected as important will be assessed via visual analysis of scatterplots depicting the prediction stratified by the variables in the interaction.

All analyses will be completed in the R statistical environment version 4.2.0 or higher.

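### Pretest and posttest use different phrases, the allocation of phrases to phases is not stated, and the tests of change carry no phrase-level error; if the lists were fixed, a list difference can pass for a change in intelligibility

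*Combined protocol and SAP*

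**What the plan says.** In the Experimental Protocol (Perceptual Training Protocol), listeners at pretest were "asked to transcribe each phrase ($n = 20$) after hearing it once". After familiarization came the posttest, "identical in structure to the pretest, except participants were asked to transcribe 60 new phrases spoken by the same speaker". The two phrase sets therefore do not overlap. The only random allocation described is of listeners, who were "randomly assigned to one of the speaker-specific training conditions".

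The Statistical Analysis Plan (Transcript Analysis, the same for both age groups) scores each phase as a percentage, "yielding a pretest PWC score and a posttest PWC score for each listener". For younger listeners, "Paired-samples t-tests will be used to test for average intelligibility improvement from pretest to posttest", with Cohen's d for each speaker condition. For older listeners, "Intelligibility improvement between the pretest and posttest will be evaluated for each speaker condition using repeated-measures ANOVA with Cohen's d effect size estimates", and the stated purpose is "to test for significant and meaningful intelligibility change due to the perceptual training".

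No phrase or list term appears in either test. The document is silent on how phrases were assigned to phases and on whether the two sets were of equal difficulty.

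**The concern.** A pre-post comparison needs both scores to be on one scale. Here each score also depends on which phrases were used. If every listener in a speaker condition heard the same 20 phrases and then the same 60, the mean change is the listeners' change plus the difference in difficulty between the two sets. That difference is the same for all listeners, so it does not enter the spread of their change scores, and a test whose error comes from that spread cannot detect it. Adding listeners shrinks the standard error but leaves the gap untouched.

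Three results are exposed: the estimated mean change, Cohen's d (numerator shifted, denominator built from listeners only), and any standard error or interval taken from the paired test or ANOVA. The difference in list length is not itself a bias in mean PWC. It only makes the pretest score noisier. The issue is difficulty.

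**Working it through.** The plan gives no sample size, significance level, variance or phrase-difficulty figure, so there is no stated figure to reproduce.

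**Inputs from the document:** 20 pretest phrases; 60 new posttest phrases; one PWC per listener per phase; tests run by speaker condition.

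**Assumed inputs:** two-sided 5% level; n = 40 listeners per condition (20 also shown); SD of listeners' change scores 7.6 points (10 and 12 also shown); phrase-difficulty SD 5 to 20 PWC points; phrases unmatched; no true change.

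**Step 1: chance gap between two fixed lists.** SD of gap = phrase SD × √(1/20 + 1/60) = phrase SD × 0.258.

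| Phrase SD | SD of gap | 95% range |
|---|---|---|
| 5 | 1.3 | ±2.5 |
| 10 | 2.6 | ±5.1 |
| 15 | 3.9 | ±7.6 |
| 20 | 5.2 | ±10.1 |

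**Step 2: what the planned test sees.** SE = 7.6/√40 = 1.20. The true SD of the mean change over possible lists is √(SE² + gap SD²). For phrase SD 5 this is √(1.20² + 1.29²) = 1.76; for phrase SD 20 it is √(1.20² + 5.16²) = 5.30. The planned standard error is therefore too small by a factor of about 1.5 (1.76/1.20) to 4.4 (5.30/1.20).

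**Step 3: rejection with no true change.** Rate = 2 × P(Z > 1.96 × SE / true SD). For phrase SD 5: 1.96 × 1.20/1.76 = 1.34, giving 18%. For phrase SDs 10, 15 and 20 the rates are 41%, 56% and 66%. Simulating the t-test itself gives 39%, 54% and 65% for the same three, slightly lower because the t critical value is larger. With 20 listeners the simulated rates are 27%, 41% and 52%. The gap is symmetric about zero, so half of each figure is false improvement and half false worsening. At n = 40 and phrase SD 10 that is about 20% false improvement.

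**Step 4: sensitivity to the change SD.** At n = 40 and phrase SD 5, the same formula falls from 18% (SD 7.6) to 13% (SD 10) and about 11% (SD 12).

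**Step 5: other ways of allocating phrases.** A second simulation had no training effect, a listener-by-phrase residual SD of 30 points (so change SD 30 × 0.258 = 7.75), n = 20, 40 or 80 and phrase SD 0 to 20. Phrases drawn afresh for each listener gave rejection rates of about 0.04 to 0.06. Four 20-phrase blocks with the pretest block rotated across listeners gave about 0.02 to 0.05. Fixed lists at phrase SD 10 gave 0.25, 0.39 and 0.53 for n = 20, 40 and 80, rising with the number of listeners.

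**Step 6: reach.** The elastic net models are run separately by speaker. A gap constant within a speaker goes into the intercept and leaves the predictor effects alone. The problem falls on the pre-post tests and Cohen's d.

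**The case against.** The strongest reply is that the premise is unknown. The file calls itself a protocol summary and does not say that lists were fixed. If phrases were drawn or rotated per listener, the tests keep their level. This stands: the document shows an unstated allocation and a test that is exposed to it, not a demonstrated error. A reader might infer that the p-values are too small as designed. The text does not support that. Even with fixed lists the error can go either way, because a harder posttest list would hide a real gain.

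The size rests on assumed values. This also stands. Matched lists, a larger change SD or fewer listeners all bring the rates down, and the two-sided rates should not be read as rates of spurious training benefit.

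A reader might also expect list error to appear as a training gain specific to one speaker. Gaps could differ by speaker, but neither age group's plan specifies a between-speaker comparison of gain, so no planned test would report it.

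Finally, the tests of change are labelled initial analyses, and the absence of an untrained group already limits attribution to training. Both are true. What remains distinct is whether the two PWC scores are comparable and whether the error term is right. Measuring change is a stated purpose of the phases, and the older-listener section draws a training conclusion from this test.

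**Conclusion.** The point holds conditionally. It is certain from the text that the phrase sets differ, that their allocation is not described, and that both tests of change use listener-only error. If lists were fixed within a speaker condition, mean change and Cohen's d carry a list-difference bias of unknown sign, and intervals from the planned tests are too narrow. With 40 listeners, change SD 7.6, phrase SD 5 to 20, unmatched lists and no true change, two-sided rejection is about 18% to 65%, about half of it false improvement, and lower if the change SD is larger. If phrases were drawn or rotated per listener, there is no inflation. The predictive models are largely unaffected. The point goes beyond a missing detail because a better analysis of the same transcripts is available under any of these allocations.

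**What to change.** Replace the paired t-test and the repeated-measures ANOVA, for each age group and speaker condition, with a phrase-level mixed logistic model. The outcome is words correct out of words in the phrase. Phase is the fixed effect, with crossed random effects for listener (intercept and phase slope) and phrase. Base the estimate of change and its interval on this model.

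State how phrases were allocated to phases: fixed, drawn per listener, rotated or matched. If they were fixed, report any evidence that the lists were of equal difficulty. Say also that the model treats the phrases as a sample and widens the interval accordingly, but cannot separate list difficulty from training. In that case, qualify the older-listener purpose statement, "to test for significant and meaningful intelligibility change due to the perceptual training".

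Rotating 20-phrase blocks across listeners would make list difficulty cancel, but it applies only to data not yet collected. The protocol describes the sessions in the past tense.

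Cost: phrase-level scoring from transcripts already in hand, a more involved model, and wider intervals for change if the lists were fixed. No new data are needed.

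### If pretest PWC is a covariate in the improvement models, whole-model R² and RMSE include pretest's own prediction and need a pretest-only reference on the same folds

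*Combined protocol and SAP*

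**What the plan says.** In the Statistical Analysis Plan, the Transcript Analysis paragraphs for Younger Listeners and for Older Listeners both define the second outcome as "intelligibility improvement (posttest PWC after accounting for pretest PWC". Neither says how the adjustment is made.

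The purpose of the models is stated in terms of listener abilities. For younger listeners the elastic nets "will assess the ability of the cognitive measures to predict both initial intelligibility and intelligibility improvement". For older listeners they are to "assess how well the cognitive measures and hearing acuity predict initial intelligibility and intelligibility improvement".

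Accuracy is judged on the whole model. The younger section says: "Predictive accuracy includes the root mean squared error (RMSE) and R^2 values for the cross-validated predictions". The older section says that the same two measures "will be used to evaluate the predictive accuracy of the cross-validated predictions".

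The younger plan fits two specifications per speaker, one without and one with pairwise interactions. The older plan fits one specification, with interactions, and counts four models in all. Neither lists a model containing pretest PWC alone.

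Both plans add variable importance by permutation, which the younger section describes as "a permutation method wherein each variable is randomly permuted". Both also plan Pearson correlations. In the younger section these cover each cognitive measure's "relationship with intelligibility (both initial and improvement) by speaker condition". In the older section they are run "to assess the correlation between the variables of interest (e.g., cognitive scores, intelligibility".

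**The concern.** The question is how well cognition, and hearing for older listeners, predict improvement. A cross-validated R² answers it only if what is being predicted, or what it is compared with, has pretest removed.

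Pretest and posttest are transcription scores from the same listener hearing the same speaker, so some correlation between them is to be expected. If the model regresses posttest PWC on pretest PWC plus the listener scores, its R² credits that correlation to the model as a whole. RMSE is lowered in the same way. An improvement model could then report a respectable R² when the listener scores contribute nothing, and the plan names no reference value that would reveal this.

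What is at stake is the interpretation of the improvement models' headline accuracy, for each speaker in each age group.

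**Working it through.** **1. The plan's own count.** For older listeners, 2 speaker conditions × 2 outcomes = 4 models, which reproduces the stated total. All four are used up, so no pretest-only model is among them. Neither of the two younger specifications is pretest-only either.

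**2. Large-sample result under the covariate reading.** Let r be the pretest–posttest correlation within a speaker condition (not in the documents; assumed). If the listener scores add nothing beyond pretest:

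- R² = r², giving 0.16, 0.36 and 0.64 for r = 0.4, 0.6 and 0.8.
- RMSE divided by the posttest SD = √(1 − r²), giving 0.92, 0.80 and 0.60.

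These are limits. Cross-validated values in small samples fall below them, noticeably so at low r.

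**3. Simulation at plausible sizes.** All inputs are assumptions except the 10-fold cross-validation (younger section) and the six scores (the table of NIH Toolbox tasks: hearing plus five cognitive measures).

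- Posttest = r × pretest + noise.
- Six scores intercorrelated 0.3, unrelated to pretest, with zero effect on posttest.
- Elastic net with main effects, tuned by 10-fold cross-validation.
- R² = 1 − SSE/SST on pooled held-out predictions.
- Pretest-only = ordinary regression on the same folds.
- 500 data sets per cell; Monte Carlo standard error at most 0.008.

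Whole-model R², with pretest-only R² in brackets:

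| Listeners per speaker | r = 0.4 | r = 0.6 | r = 0.8 |
|---|---|---|---|
| 30 | 0.05 (0.06) | 0.25 (0.27) | 0.56 (0.58) |
| 50 | 0.08 (0.09) | 0.29 (0.31) | 0.59 (0.60) |
| 80 | 0.11 (0.12) | 0.31 (0.32) | 0.61 (0.62) |

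A separately written repeat at 50 listeners gave 0.08, 0.26 and 0.58, against 0.09, 0.28 and 0.59 for pretest alone. A smaller run with five null scores (50 listeners, 40 data sets per value) gave 0.14, 0.40 and 0.77 at r = 0.5, 0.7 and 0.9, against 0.17, 0.42 and 0.78.

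With a pretest-residualised outcome and the same null scores, R² was −0.06 to −0.02 over the nine cells of the table. That reading correctly shows no prediction.

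**4. What a difference from pretest-only would show.**

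- *Zero effect:* the difference in R² averaged −0.02 to −0.01. The RMSE reduction was −0.014 to −0.005 posttest SD.
- *True effect of 20% of the variance left after pretest:* the population increment is 0.20 × (1 − r²), that is 0.20 × 0.84 = 0.17, 0.20 × 0.64 = 0.13 and 0.20 × 0.36 = 0.07. The simulated difference in R² averaged 0.04 to 0.13 over the same sizes. The RMSE reduction was 0.031 to 0.075 posttest SD.

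On average the difference separates no effect from a real one, though it understates the latter.

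**5. The null difference is not exactly zero.** It depends on how pretest is treated:

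| Pretest | Main effects | With interactions |
|---|---|---|
| Penalised | −0.02 to −0.01 | −0.07 to 0.04 |
| Unpenalised | 0.001 to 0.013 | 0.003 to 0.065 |

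The unpenalised values are largest at 30 listeners. The interaction runs used 60 data sets per cell (standard error at most 0.023).

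**The case against.** **The text may not mean a covariate.** The PWC scores are said to quantify improvement, which suggests one value per listener. The younger plan's correlations with improvement need such a value. The predictors named are cognition, plus hearing for older listeners; pretest PWC is never listed. All of this stands, and it makes the point conditional. A reader might infer that the planned R² is inflated as written. The documents do not support that, because a residual outcome is equally open and has no such problem. But adjusting posttest for pretest is also the ordinary description of a covariate, so that reading cannot be set aside.

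**Permutation importance already exposes pretest's share.** Largely true. At 50 listeners, r = 0.6 and zero effect, permuting pretest costs about 0.59 in R². The six scores together cost 0.06 to 0.08 on fitted data, or 0.016 on held-out data. The plan does not say which data are used, though in the younger section the definition of importance directly follows that of cross-validated accuracy, so held-out is the more natural reading. A reader would therefore see that pretest dominates, and it would be wrong to infer that cognition's part is hidden altogether. But importance works one variable at a time. The plan does not propose adding the drops up, and at 30 listeners even the held-out sum was 0.05 to 0.12 under zero effect. It also leaves the reported R² and RMSE as they are.

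**The planned correlations could show the pretest–posttest association.** In the older section they may. They are in-sample, so they are not on the same footing as a cross-validated R², and the plan does not propose comparing the two.

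**The models are supplementary.** The SAP presents them as a way to understand the patterns more fully, and no decision threshold rests on R². This stands and limits the weight of the point.

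**Conclusion.** The point holds in conditional form. If pretest PWC is a covariate, whole-model cross-validated R² and RMSE do not measure how well cognition and hearing predict improvement. With an assumed 50 listeners per speaker and r of 0.4, 0.6 and 0.8, R² is about 0.08, 0.26–0.29 and 0.58–0.59 when the listener scores add nothing, within about 0.02 of pretest alone. Sample size, correlations and score structure are all assumed. The mechanism does not depend on them, but the size does: at 30 listeners and r = 0.4 the figure is only 0.05.

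Three stronger conclusions are tempting and should not be drawn:

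- *R² will simply equal the squared correlation.* That is the large-sample limit; at r = 0.4 the limit is 0.16 and the simulated values are 0.05 to 0.11.
- *Covariate, residual and gain-score R² values can be set side by side to show how far the results would differ.* They have different outcome variances in the denominator, and any contrast rests on an assumed relation between cognition and pretest that the documents do not give.
- *The evidence for a training effect is compromised.* The pretest-to-posttest tests do not use these models, and the initial-intelligibility models have no pretest adjustment.

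The unstated form of adjustment would, by itself, be only a missing detail. The substantive gap is the absence of a pretest-only reference under a reading that the wording allows.

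**What to change.** In the improvement models of both SAP sections:

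- **If pretest PWC is a covariate,** fit a pretest-only regression on the same cross-validation folds for each speaker. For each model specification, report the difference in cross-validated R² and RMSE between the full model and this reference as the accuracy of cognition and hearing. Label the whole-model R² as including pretest.
- **State in advance whether pretest is penalised,** since that choice shifts the null difference and, for main effects, changes its sign. Do not read small differences as prediction.
- **If a residual outcome is used instead,** say so, and estimate the regression of posttest on pretest within each training fold, so that held-out listeners do not inform their own adjustment.

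The cost is one simple regression per speaker (two extra fits for older listeners, on top of the four planned), a sentence or two of specification per section, and a reported figure that will look less favourable than the whole-model R². No new data are needed.

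### Does the lack of a stated cut-off for calling an elastic-net interaction important require a change to the plan?

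*Combined protocol and SAP*

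**What the plan says.** **Younger Listeners, Statistical Analyses.** Elastic net models predict initial intelligibility and improvement separately for each speaker. "For each speaker, two model specifications will be used: 1) main effects only and 2) main effects and all two-way interactions". On tuning: "Model-specific hyper-parameters will be selected based on 10-fold cross-validation". On accuracy: "Predictive accuracy includes the root mean squared error (RMSE) and R^2 values for the cross-validated predictions". On importance: "Variable importance will be extracted from each model using a permutation method wherein each variable is randomly permuted"; the measure is the resulting change in accuracy. Predictions, importance metrics and post hoc assessment together "will inform on the nature of the important interactions".

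**Older Listeners, Statistical Analysis.** Four models are fitted, each with every main effect and every pairwise interaction, and hearing joins the predictors. No main-effects-only model is specified. "The elastic net models will be evaluated using the model accuracy and variable importance metrics". "Variable importance will be extracted from each model using permutation". "Post hoc assessments will also be conducted to evaluate the nature of the important main effects and interactions". The assessment is visual, by scatterplots of the model prediction. RMSE and R² again refer to cross-validated predictions.

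Neither section gives an importance cut-off, a null reference, or an accuracy condition to be met before an interaction is read. The opening paragraph of the SAP presents the predictive work as an addition to the pretest-posttest comparison.

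**The concern.** Both sections assume a selection step that neither defines. Each model has many candidate interactions, and minimum-error tuning often keeps noise terms with small non-zero coefficients. If a reader or analyst treated every kept term with positive importance as a finding, chance patterns could be reported as pairs of listener traits that jointly predict intelligibility. The older plan looks more exposed: it has four models and no main-effects comparator, and plots of the prediction show what the model fitted without showing whether the observed scores support it. The tuning rule (minimum error or one standard error) and the shuffled unit (model column or parent measure) are also unstated. What is at stake is the interpretation of interactions; the tests of improvement after training do not use these models.

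**Working it through.** **1. The plan's own figure.** Two speaker conditions × two outcomes = 4 older-listener models, as stated.

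**2. Number of terms.** With p predictors the interaction model has p + p(p−1)/2 terms. The Perceptual Training Protocol section lists five cognitive constructs: 5 + 10 = 15 terms. Adding hearing for older listeners: 6 + 15 = 21. If pretest PWC also entered the improvement models as a predictor with interactions, the counts would be 6 + 15 = 21 and 7 + 21 = 28. The plan does not settle this.

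**3. Assumptions, none of them in the documents.** n per model 30 to 100; predictors correlated 0.3 or 0.6; residual SD 1; 10-fold cross-validation; importance scored on held-out folds; no true interaction unless stated. The one main effect is 0.5; the three are 0.6, 0.6 and 0.4.

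**4. Share of models with at least one noise interaction flagged.**

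| Rule | No signal | One main effect | Three main effects |
|---|---|---|---|
| Positive importance, minimum-error tuning | 30-46% | 53-62% | 60-76% |
| Same, and CV R² above 0 | 13-24% | 43-59% | 60-75% |
| Same as first row, and beats main-effects model | 23-34% | 24-32% | 18-27% |
| At least 50% of the largest importance | 25-40% | 3-32% | 0-15% |
| Positive importance, 1-SE tuning | 0-8% | 7-18% | 15-45% |

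There were 1,166 data sets per cell, so the simulation SE is at most √(0.25/1166) = 1.5 points. A second simulation (n = 30 to 150, correlation 0.3) gave 35-51% with no signal and 61-74% with main effects under the first rule, and 20-40% once the interaction model also had to beat the main-effects model.

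Over four independent models, a per-model rate of 0.40 gives 1 − 0.60⁴ = 0.87. Direct simulation of the older design with no signal gave 83-91%. Both figures use the most lenient rule.

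**5. A sensible fill-in.** Requiring CV R² above 0, better accuracy than the main-effects model, and at least half the largest importance gave 0-27% overall and 0-8% with three main effects. This was a small run of 48 data sets per cell, with SE at most √(0.25/48) = 7.2 points.

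**6. What a formal reference buys and costs.** The reference is the 95th percentile of the maximum interaction importance, from refits with permuted main-effects residuals. It gave noise-flag rates of 4.6-4.7% per model in one run and 3.5-6.0% in another. Detection of a true 0.5 SD interaction was:

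| n | Positive importance | Per-model reference | Group-wide reference |
|---|---|---|---|
| 30 | 70% | 12-15% | 2% |
| 50 | 85% | 31-41% | 18% |
| 100 | 100% | 77-90% | 70% |

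The per-model loss is 55 to 58 points at n = 30 (70 − 15, 70 − 12) and 44 to 54 points at n = 50 (85 − 41, 85 − 31). With no threshold at all, the true interaction ranked first among the interactions in 53%, 65% and 95% of data sets. Main effects suffer too: at n = 50, true effects of 0.4 to 0.6 passed an outcome-permutation reference in only about 44-57% (56 data sets, SE up to about 7 points).

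**7. The other unstated choices.** Both sections speak of interactions as individually important, which fits shuffling model columns and not parent measures. Under the parent reading the positive-importance rates are much the same (29-45%, 50-57% and 63-73%). Both sections define accuracy on cross-validated predictions, which points to held-out scoring in each.

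**The case for a change.** The strongest case for a change is that the spread is itself the problem: from near 0% to about 75% per model, depending on a rule the reader cannot see. Cross-validated accuracy describes the whole model and is not tied to reading any one term. The comparator exists only for younger listeners and has no stated decision attached. Even where the interaction model must beat it, 18-34% of models still flag noise, and 55-80% do when one true interaction lets the model pass. One sentence calling interaction results hypothesis-generating would cost nothing.

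The omission stands, and so does the weaker position of the older plan. The step from there to a defect does not. The high rates belong to a rule that the plan never states, under sample sizes that it does not give. The plan attaches no p-value or error rate to an interaction, so family-wise control is a standard brought in from outside. A label or a written tuning rule would record detail and alter no analysis. Timing also matters: the file is dated 7/11/24, describes the sessions in the past tense, and already reports that the older data failed parametric assumptions. A threshold added now could not clearly count as prespecified.

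**Conclusion.** No change follows. The plan leaves unwritten how an interaction comes to be called important, within a supplementary predictive analysis. It does not prescribe a rule that gives a wrong answer. The chance of interpreting a noise interaction is unknown: near 0% under strict rules, about 75% per model under a bare positive-importance rule, and 0-27% under the combined fill-in. For younger listeners that fill-in draws on two things already planned, cross-validated R² and the main-effects model; for older listeners analysts would have to fit the comparator themselves. The formal remedy holds noise near 5% per model but gives up 44 to 58 points of detection at n of 30 to 50, which is a fair trade-off to decline in exploratory work. These figures assume n of 30 to 100, the signals listed above, and pretest PWC not entering as a predictor with interactions. The conclusion would weaken if interactions were reported as confirmed findings on positive importance alone, but nothing in the SAP commits the analysts to that.
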